#### 8.3.6. Subgroup Analyses

Subgroup analyses for all secondary endpoints will be reported for the On-Study Estimand based on the groupings defined in Section 8.2.6. However, analyses of QoL-B which is applicable for adults only, will exclude the adolescent subgroup. In addition, the main analysis for secondary endpoints will be repeated for the adolescent subgroup (12-<18 years of age), and separately for the adult subgroup for the On-Study estimand.

Subgroup analysis will be displayed in tabulations and forest plots.

#### **8.4.** Intercurrent Event Assessment

The frequency and percentage of participants experiencing each of the ICE types (see Section 6.2.1) will be tabulated by treatment group. The ICE of addition of a new chronic antibiotic will be further broken down by its subtypes, if applicable. In addition, the time to first ICE will be analyzed in a manner like the analysis of time to first PE, including a plot of the complement (1 – Kaplan-Meier estimates) (see Section 8.3.1.1).

CONFIDENTIAL Page 64 of 139

## 8.5. Exploratory Endpoints

In participants with NCFBE, the exploratory objectives are as described in protocol section 2.3.

**Table 8: Exploratory Endpoints** 

Variable	Population Level Summary	Estimand Name	Treatment Regimen	ICEs/ Strategy	Section
Average Daily Change from Baseline in Bronchiectasis Exacerbation and Symptom Tool (BEST) score Over the 52-Week Treatment Period	Mean Difference	On-Study	Assignment to IP regardless of discontinuation or modifications to standard of care	Early discontinuation from randomized IP / Treatment Policy Modification to standard of care / Treatment Policy	8.5.1
Duration of exacerbation events that meet the protocol definition of PE diagnosis Over the 52- Week Treatment Period	Mean Difference	On-Study	Assignment to IP regardless of discontinuation or modifications to standard of care	Early discontinuation from randomized IP / Treatment Policy Modification to standard of care / Treatment Policy	8.5.2
Days Hospitalized for Adjudicated PEs per patient year Over the 52-Week Treatment Period	Mean Annualized Rate	On-IP	Randomized IP regardless of modifications to standard of care	Early discontinuation from randomized IP / While On-Treatment	8.5.3
Days of Absence from Work/School Related to Adjudicated PEs per Patient Year Over the 52-Week Treatment Period	Mean Annualized Rate	On-IP	Randomized IP regardless of modifications to standard of care	Early discontinuation from randomized IP / While On-Treatment	8.5.4

CONFIDENTIAL Page 65 of 139

Change from Baseline in prebronchodilator and postbronchodilator FEV 1 , forced vital capacity (FVC), peak expiratory flow rate (PEFR), percent predicted forced expiratory flow in 1 second (ppFEV 1 ) and forced expiratory flow between 25% and 75% of forced vital capacity (FEF [25-75%] ) at Weeks 16, 28, 40, and 52	Mean Difference	On-Study	Assignment to IP regardless of discontinuation or modifications to standard of care	Early discontinuation from randomized IP / Treatment Policy Modification to standard of care / Treatment Policy	8.5.5
Outpatient Visits, emergency room (ER) visits, and hospitalizations for any reason	Mean Annualized Rate	On-IP	Randomized IP regardless of modifications to standard of care	Early discontinuation from randomized IP / While On-Treatment	8.5.6
Change in QOL-PCD Domain Scores From Baseline to Weeks 16, 28, 40, and 52 in Adolescent Participants (≥12 to <18 Years of age) with PCD	Mean Difference	On-Study	Assignment to IP regardless of discontinuation or modifications to standard of care	Early discontinuation from randomized IP / Treatment Policy Modification to standard of care / Treatment Policy	8.5.10
Change from Baseline in EuroQoL-5 Dimension-5 Level Questionnaire (EQ-5D-5L) score to Week 52	Mean absolute value and mean change from baseline	On-Study	Assignment to IP regardless of discontinuation or modifications to standard of care	Early discontinuation from randomized IP /Treatment Policy Modification to standard of care/ Treatment Policy	8.5.8

CONFIDENTIAL Page 66 of 139

Change from Baseline in QoL-B Domain Scores to Weeks 16, 28, 40, and 52 in Adult participants	Mean Difference	On-Study	Assignment to IP regardless of discontinuation or modifications to standard of care	Early discontinuation from randomized IP /Treatment Policy Modification to standard of care/ Treatment Policy	8.5.9
PGI-C and the Change from Baseline in PGI-S at Weeks 16, 28, 40, and 52 in Adult participants	Mean Difference	On-Study	Assignment to IP regardless of discontinuation or modifications to standard of care	Early discontinuation from randomized IP /Treatment Policy Modification to standard of care/ Treatment Policy	8.5.10
Rate of Change in Prebronchodilator and Postbronchodilator FEV1 Over the 52-Week Treatment Period	Slope	On-Study	Assignment to IP regardless of discontinuation or modifications to standard of care	Early discontinuation from randomized IP /Treatment Policy Modification to standard of care/ Treatment Policy	8.5.11
Change from Baseline in Bronchiectasis Scoring Technique for Computed Tomography (BEST-CT) and Airway-Artery (AA) Scores at Week 52	Mean absolute value and mean change from baseline	On- Treatment	Standard of care + randomized IP	Early discontinuation from randomized IP / While On-Treatment Early discontinuation from standard of care/ While On-Treatment	8.5.12
Change from Baseline in Concentration of biomarkers (Neutrophil Elastase [NE],	Mean Difference	On-IP	Randomized IP regardless of	Early discontinuation from randomized IP / While On-Treatment	11.1

CONFIDENTIAL Page 67 of 139

Brensocatib (INS1007) Insmed Incorporated Statistical Analysis Plan: INS1007-301

FINAL Version 1.0 19 APR 2024

Cathepsin G [CatG], Proteinase 3 [PR3]) in Sputum to Week 52			modifications to standard of care		
Change from Baseline in Concentration of biomarkers (NE, CatG, PR3, and neutrophil functions) in Blood to Week 52	Mean Difference	On-IP	Randomized IP regardless of modifications to standard of care	Early discontinuation from randomized IP / While On-Treatment	11.2

CONFIDENTIAL Page 68 of 139

## 8.5.1. Average Daily Change from Baseline in BEST Score Over the 52-Week Treatment Period

The Estimand of the average BEST Score is the On-Study Estimand in which all observed data will be included in the analysis (see Section 2). The ITT Analysis Set (see Section 5.2) will be used for this Estimand. The derivation of the endpoint is detailed in Section 6.7.5.3.

The average daily change from baseline in the BEST score over the 52-week treatment period will be analyzed with an analysis of covariance model. The model will contain main effects for treatment group, sputum sample being classified as positive or negative for *Pseudomonas aeruginosa* at Screening Visit, the number of prior PEs [<3 or ≥3] in the previous 12 months, and stratification region (North America, Europe, Japan, and the Rest of the World). The baseline BEST score will be included as a covariate. The OM option will be used to adjust the co-efficients for the LSMEANS to reflect the observed data. The adjusted means in each treatment group, the adjusted mean differences between treatments, their 95% CIs and associated p-values will be presented. Completion rates at baseline and at Week 52 will be presented (see Section 6.7.5.10).

Mean BEST score changes from baseline over time will be plotted by study day to assess trends over time. The time axis will be limited to 365 days. No tabulation will be generated.

In addition, a figure presenting the average in daily change from baseline in BEST Score, 21 days before and 21 days after a PE onset date that meet the protocol definition of PE diagnosis will be plotted. This plot will be presented by treatment group. Only participants with reported exacerbation(s) will be included into the plot. All data of participants with at least one exacerbation will be included when calculating the average in daily change from baseline in BEST Score.

Further, a summary table and a plot will be produced by treatment group where the BEST score will be averaged over a 4-week period. The assignment into the 4-week periods will follow the instructions given in Section 6.7.1.7. The time axis of the figure will be in months.

# 8.5.2. Duration of Exacerbation Events that Meet the Protocol Definition of PE Diagnosis based on Independent Adjudication Process Over the 52-Week Treatment Period

The average duration of exacerbation events that meet the protocol definition of PE diagnosis over the 52-week treatment period will be included in the analysis (see Section 2). The ITT Analysis Set (see Section 5.2) will be used. The derivation of the endpoint is detailed in Section 6.7.1.

Duration of exacerbation events that meet the protocol definition of PE diagnosis based on independent adjudication process will be summarized by treatment group using descriptive statistics.

CONFIDENTIAL Page 69 of 139

<sup>5 Note: Age group is not included into the statistical model as questionnaire is applicable to adult participants only.

## 8.5.3. Days Hospitalized for Adjudicated PEs per Person-Year Over the 52 Week Treatment Period

The number of days hospitalized for adjudicated PEs per patient year will be presented and will utilize the ITT Analysis Set (see Section 5.2). The derivation of the endpoint is detailed in Section 6.7.1.4.

The number and percentage of participants and the number of hospitalizations, including the duration of hospitalization, the person-time (follow-up time) and the number of days hospitalized per person-year will be summarized descriptively by treatment group.

# 8.5.4. Days of Absence from Work/School Related to Adjudicated PEs per Patient Year Over the 52-Week Treatment period

The number of days absent from work/school will be presented and will utilize the ITT Analysis Set (see Section 5.2). The derivation of the endpoint is detailed in Section 6.7.1.5.

The number and percentage of participants missing work/school, including the person-time (follow-up time) and the number of days missed per person-year will be summarized descriptively by treatment group.

# 8.5.5. Change from Baseline in Prebronchodilator and Postbronchodilator FEV1, FVC, PEFR, ppFEV1 and FEF25-75% to Weeks 16, 28, 40, and 52

The change from baseline in prebronchodilator and postbronchodilator FEV1, FVC, PEFR, ppFEV1 and FEF25-75% to Weeks 16, 28, 40, and 52 will be presented based on the ITT Analysis Set. The derivation of the endpoint is detailed in Section 6.7.3.

Assessments including the changes from baseline will be summarized by time point similar to the display of postbronchodilator  $FEV_1$  in Section 8.3.3.1.

To note: postbronchodilator  $FEV_1$  will be evaluated as part of secondary endpoint analysis in Section 8.3.3.1. Outputs will show prebronchodilator for  $FEV_1$  only.

#### 8.5.6. Outpatient Visits, ER Visits, and Hospitalizations for any Reason

The outpatient visits, ER visits, and hospitalizations for any reason per patient year will be presented and will utilize the ITT Analysis Set (see Section 5.2). The derivation of the endpoint is detailed in Section 6.7.5.8.

The number of outpatient visits, ER visits, duration of hospitalization in days, and hospitalizations for any reason per patient year will be summarized by treatment group using descriptive statistics.

# 8.5.7. Change in QOL-PCD Domain Scores from Baseline to Weeks 16, 28, 40, and 52 in Adolescent Participants (≥12 to <18 Years of age) with PCD

The change from baseline in QoL-PCD Domain scores at 16, 28, 40, and 52 weeks in adolescents will be presented and will use the ITT Analysis Set.

QoL-PCD Domain scores and changes from baseline will be summarized and statistically analyzed similar to the analysis of QoL-B Respiratory Symptoms Domains score in

CONFIDENTIAL Page 70 of 139

Section 8.3.5.1. As adolescents will have data only, the age group will be removed from the statistical model. Completion rates will be presented by time point (see Section 6.7.5.10).

### 8.5.8. Change from Baseline in EuroQoL-5D-5L Score to Week 52

EuroQoL-5D-5L index score and VAS overall self-rated health status score will be summarized as observed values and changes from baseline at each visit. Changes from baseline will be statistically analyzed similar to the analysis of QoL-B Respiratory Symptoms Domains score in Section 8.3.5.1.

The percentage of participants' categorical responses to each of the 5-dimensions will be tabulated. VAS and index scores and changes from baseline will be summarized and statistically analyzed similar to the data evaluation of postbronchodilator FEV1 in Section 8.3.3.1. Completion rates will be presented by time point (see Section 6.7.5.10).

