#### **Study Design:**

This is a Phase 3, randomized, double-blind, placebo-controlled, parallel-group, multicenter, multinational study to assess the efficacy, safety, and tolerability of 2 dosage strengths of brensocatib compared with placebo in subjects with non-cystic fibrosis bronchiectasis (NCFBE). Approximately 1620 adult subjects, defined as subjects ≥18 to ≤85 years of age, will be randomized in a 1:1:1 ratio to 3 treatment arms (540 subjects per arm) to receive brensocatib 10 mg once daily (QD), brensocatib 25 mg QD, or matching placebo QD for 52 weeks.

- Randomization will be stratified based on geographic region (North America, Europe, Japan, and the Rest of the World), sputum sample being classified as positive or negative for *Pseudomonas aeruginosa* at Screening Visit, and the number of prior PEs (2, or ≥ 3) in the previous 12 months.
- Randomization will be enforced to have approximately 30% of adult subjects with 3 or more prior PEs, to have no more than 20% of subjects older than 75 years of age, to have approximately no more than 20% of subjects with eosinophil count in peripheral blood ≥300/mm³ at Screening, and to have no more than 20% of subjects with COPD as comorbidity.
- Enrollment targets have been established for adult subjects with up to 13% of subjects from Eastern Europe and with North America, Western Europe, Asia Pacific, and Latin America contributing between 20% and 30% each. No single country (except the US) will contribute more than 15% of the overall randomized population.

For this study, the adolescent population is defined as subjects ≥12 to <18 years of age at Screening. Adolescent subjects are required to have at least 1 PE in the prior 12 months. Approximately 40 adolescent subjects will be randomized in a 2:2:1 ratio to 3 treatment arms (16:16:8 subjects per arm, respectively) to receive brensocatib 10 mg QD, brensocatib 25 mg QD, or matching placebo QD for 52 weeks. Sputum sample will be classified as positive or negative for *Pseudomonas aeruginosa* at Screening Visit. Subjects in this age group who are not able to produce a sputum sample will be marked as negative. No stratification will be applied to this age group.

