# 1. INTRODUCTION AND BACKGROUND INFORMATION

## 1.1. Non-Cystic Fibrosis Bronchiectasis

Non-cystic fibrosis bronchiectasis (hereafter referred to as NCFBE) is a chronic inflammatory disease defined by permanent dilatation of the bronchi (Barker, 2002). Subjects suffer from daily cough and sputum production and experience frequent exacerbations. The prevalence of NCFBE has steadily increased over the past 10 years in both the United States and Europe (Henkle et al., 2018; Quint et al., 2016). Despite an urgent need for treatment that can break the cycle of inflammation, infection, and irreversible progressive lung damage, there are no approved therapies specifically targeting this disease.

A European study (Lonni et al., 2015) included a total of 1,258 patients with NCFBE enrolled within the 7 centers (median age, 67 years; age range, 18–94 years; 40% males). Among the entire study population, the etiology of bronchiectasis was identified in 60% of patients (range among cohorts, 46%–82%). Excluding idiopathic bronchiectasis, the first 5 most commonly identified etiologies were post-infective (20%), COPD related (15%), connective tissue disease related (10%), immunodeficiency related (5.8%), and asthma related (3.3%). Of note, a significantly higher prevalence of COPD-related bronchiectasis was detected in patients with severe disease (22%) in comparison to those with mild disease (2.8%) and moderate disease (8.1%), according to BSI categories (P<0.001).

In a systematic review comprising 989 children with NCFBE from 12 studies, 63% of the subjects had an underlying disorder. Infectious diseases (17%), primary immunodeficiency (16%), aspiration (10%), ciliary dyskinesia (9%), congenital malformation (3%), and secondary immunodeficiency (3%) were the most common disease categories; 999 etiologies were identified. Severe pneumonia of bacterial or viral etiology and B cell defects were the most common disorders identified (Brower et al., 2014). In a recent study of 69 children with NCFBE at a center in the Netherlands, etiology was established in 91% of patients (n=63; median age 9 [3 to 18 years]). Post-infection (29%), and immunodeficiency (29%) were most common, followed by congenital anomalies (10%), aspiration (7%), asthma (6%), and PCD (1%) (Beckeringh et al., 2019).

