#### 4.1.2. Exclusion Criteria

Subjects are not eligible to participate in the study if they meet any of the following criteria:

- 1. A primary diagnosis of COPD or asthma as judged by the Investigator. Patients with comorbid COPD and/or asthma can be enrolled if bronchiectasis is their primary diagnosis.
- 2. Subjects receiving supplemental oxygen >12 hours per day.
- 3. Bronchiectasis due to cystic fibrosis.
- 4. Current smokers as defined per CDC: an adult who has smoked 100 cigarettes in his or her lifetime and who currently smokes cigarettes.
- 5. No evidence of bronchiectasis according to the BE-CT scoring system.
- 6. Known or suspected immunodeficiency disorder, including history of invasive opportunistic infections (eg, TB, histoplasmosis, listeriosis, coccidioidomycosis, pneumocystosis, aspergillosis) despite infection resolution, or otherwise recurrent infections of abnormal frequency, or prolonged infections suggesting an immunecompromised status, as judged by the Investigator.
- 7. Known history of HIV infection.
- 8. Established diagnosis of hepatitis B viral infection at the time of Screening, or positive for HBsAg at the time of Screening.
  - Subjects who have gained immunity for hepatitis B virus infection after vaccination (subjects who are HBsAg-negative, HBsAb-positive, and HBcAb-negative are eligible for the study).
  - Subjects with positive HBcAb are eligible for the study only if hepatitis B virus DNA level is undetectable.
- 9. Established diagnosis of HCV infection at the time of Screening. Subjects positive for hepatitis C antibody are eligible for the study only if HCV RNA is negative.
- 10. Currently being treated for NTM lung infection, allergic bronchopulmonary aspergillosis, or TB.
- 11. Active and current symptomatic infection by COVID-19.
- 12. Unable to perform technically acceptable spirometry that meet the ATS/ERS acceptability criteria with at least 3 acceptable flow-volume curves, at least 2 of which meet the ATS/ERS repeatability criteria for FEV1 during Screening.
- 13. Inability to follow the procedures of the study (eg, due to language problems or psychological disorders).
- 14. Receiving medications or therapy that are prohibited as concomitant medications (see Section 5.11.1 for prohibited concomitant medications).
- 15. Started oral or inhaled antibiotics as chronic treatment for NCFBE <3 months prior to the Screening Visit.

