## 6.7.5.7. Quality of Life Questionnaire – Primary Ciliary Dyskinesia (QoL-PCD) for Adolescents

QoL-PCD has been added to ASPEN for adolescent participants in countries where translation is available (English, Spanish, Hebrew).

The QoL-PCD is separated as below:

- QoL-PCD for Adolescents (ages 13 to 17 years) includes 38 items divided into two sections, Section I: Quality of Life, and Section II. School, Work, or Daily Activities.
- QoL-PCD for Children (ages 6 to 12 years; questionnaire will be completed for participants at a year of 12 as inclusion into this study requires a minimum age of 12 years) includes 34 items.
- QoL-PCD for Parents / Caregivers (ages 6 to 12 years; questionnaire will be completed for participants at a year of 12 as inclusion into this study requires a minimum age of 12 years) includes 35 items divided into two sections, Section I: Quality of Life, and Section II. Symptoms.

The questionnaire has 9 subscales in the 13-17 years of age group: Physical Functioning (n=5), Vitality (n=3), Emotional Functioning (n=5), Treatment Burden (n=4), Upper Respiratory Symptoms (n=4), Lower Respiratory Symptoms (n=6), Role (n=4), Social Functioning (n=3), Hearing Symptoms (n=2).

CONFIDENTIAL Page 45 of 139

Scoring will be performed as indicated in Appendix B. The QoL-PCD will be collected at Study Day 1, at Week 4, Week 16, Week 28, Week 40, Week 52 (EOT) and Week 56 (EOS).

Baseline is defined as the most recent assessment on or before study day 1.

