In addition, mean of %change (+/- SD) values over time will be produced by parameter using scheduled sampling time by dose level overlaid in the same figure. Further, the %change profiles will be produced over time displaying NE, CatG, and PR3 activities side by side in box plots by treatment group.

CONFIDENTIAL Page 84 of 139

# 11.2. Change in Concentration of Biomarkers (NE, CatG, PR3) in Blood to Week 52

The analysis of concentration of biomarkers in sputum in Section 11.1 will be repeated for concentration of biomarkers in blood, except the statistical analysis which will not be produced due to the limited number of participants.

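### SAP 8.5.7 plans a model-based placebo comparison of QoL-PCD in adolescents with PCD, a subgroup probably too small for the contrast to be estimated or for its sandwich intervals to hold their level

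*SAP*

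**What the plan says.** Protocol 2.3, exploratory objective 7, asks for the effect of brensocatib versus placebo on QoL-PCD domain scores in adolescents with PCD. SAP Table 8 gives the population-level summary as a mean difference. SAP 8.5.7 states the method: "QoL-PCD Domain scores and changes from baseline will be summarized and statistically analyzed similar to the analysis of QoL-B" Respiratory Symptoms in SAP 8.3.5.1. The only modification it names is dropping an age-group term, which the 8.3.5.1 model does not contain.

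The 8.3.5.1 model has treatment, visit, treatment-by-visit, *P. aeruginosa* status, prior PEs, four-level region and baseline. It uses compound symmetry with a sandwich variance and reports differences, 95% intervals and p-values. Its fallback applies only when the model fails to converge.

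On who contributes data:
- Protocol, Study Design: "Approximately 40 adolescent subjects will be randomized in a 2:2:1 ratio to 3 treatment arms (16:16:8 subjects per arm, respectively").
- Protocol 7.5.5 limits the questionnaire to adolescents in whom PCD is the cause of NCFBE and for whom a validated translation exists.
- SAP 6.7.5.7: "QoL-PCD has been added to ASPEN for adolescent participants in countries where translation is available (English, Spanish, Hebrew"). It uses separate forms for age 12 and ages 13 to 17; SAP Tables 13 and 14 give them nine and seven domains with different items.

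For blood biomarkers, measured in about 40 adults, SAP 11.2 repeats the sputum displays "except the statistical analysis which will not be produced due to the limited number of participants".

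**The concern.** The model was written for the adult QoL-B data, from a trial of about 1620 adults. Section 8.5.7 carries it over to a subgroup that cannot exceed about 40 and is probably far smaller. It sets no minimum number per arm, no reduced model and no descriptive-only rule.

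Two failures are possible. If an arm is empty, or if there are fewer participants than between-subject parameters, the dose-versus-placebo contrast cannot be estimated. If somewhat more participants enrol, the contrast can be estimated, but a sandwich variance built from a few participants understates uncertainty. The second case matters more: it yields ordinary-looking intervals and p-values, for up to nine domains, that do not hold their nominal level. A reader could then take a chance difference as evidence of a paediatric quality-of-life effect.

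**Working it through.** **1. Reproduce the planned allocation.** 40 × 2/5 = 16, 40 × 2/5 = 16, 40 × 1/5 = 8. This matches the plan's 16:16:8.

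**2. PCD shares.** The only figures in the documents are two background shares in Protocol 1.1: 9% in a systematic review of 989 children ("aspiration (10%), ciliary dyskinesia (9%), congenital malformation (3"%) and 1% in a single-centre study of 69 children ("asthma (6%), and PCD (1"%). Exclusion criterion 6 bars "Known or suspected immunodeficiency disorder", which raises the PCD share among those eligible:
- Review: primary 16% + secondary 3% = 19% removed, so 9/81 = 11.1%.
- Single centre: 29% removed, so 1/71 = 1.4%.

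**3. Expected numbers.** Total = 40p; placebo = 8p; P(none on placebo) = (1 − p)^8, taking exactly eight adolescents on placebo and independent PCD status.

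| Share p | Total | Placebo | P(none on placebo) |
|---|---|---|---|
| 1% | 0.40 | 0.08 | 0.92 |
| 1.4% | 0.56 | 0.11 | 0.89 |
| 9% | 3.6 | 0.72 | 0.47 |
| 11.1% | 4.4 | 0.89 | 0.39 |

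One expected placebo respondent needs p = 1/8 = 12.5%. The translation limit and the two questionnaire forms reduce the number in any one analysis. So may the primary database lock, which does not wait for adolescents to finish (SAP 4.2).

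**4. Model size.** With the four endpoint visits (Weeks 16, 28, 40, 52), the fixed effects are intercept 1 + treatment 2 + visit 3 + interaction 6 + *P. aeruginosa* 1 + prior PEs 1 + region 3 + baseline 1 = 18. Nine of these are between-subject (1 + 2 + 1 + 1 + 3 + 1). Four or five participants cannot identify nine between-subject effects.

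**5. Simulation of the full model under no treatment effect.** The contrast is 10 mg versus placebo at Week 52, with a sandwich standard error and a t reference on within-subject degrees of freedom. Assumptions not in the documents: compound-symmetric correlation 0.5 (treated as known); region 30/35/5/30%; *P. aeruginosa* positive 20%; three or more prior PEs 30%; no missing visits. Runs of 1000 to 2000 per size, with ranges where repeated runs differed:

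| Arms (10 mg:25 mg:placebo) | Contrast estimable | Coverage of nominal 95% interval, when estimable |
|---|---|---|
| 2:2:0 or 1:1:1 | never | – |
| 2:2:1 | about 5% of runs | too few runs to quote |
| 3:3:2 | about 74% | about 42 to 43% |
| 5:5:2 | about 98% | about 67 to 70% |
| 8:8:4 | all | about 82 to 86% |
| 16:16:8 | all | about 90 to 91% |

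The 5:5:2 row corresponds to an assumed PCD share of 30% (16 × 0.30 = 4.8 and 8 × 0.30 = 2.4). The 8:8:4 row needs a share of 50%, and the last row needs every adolescent to have PCD.

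**The case against.** **The count is not in the plan.** A reader might infer that the enrolment plan itself yields fewer than one placebo respondent. It does not. The plan fixes about 40 adolescents; the 1% and 9% come from background literature on children, not from 12-to-17-year-olds at the selected sites. The sponsor surveyed sites with paediatric experience and added the PCD endpoint in the same amendment as the adolescents, so a higher share is plausible. This stands, and the counts above are conditional. It does not rescue the method, because coverage is still below nominal if all 40 have PCD.

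**Spurious significance is not the usual result.** A reader might also infer that false positive findings are likely. At the sizes implied by the background shares, the usual outcome is a contrast that cannot be estimated, which misleads nobody. Misleading intervals require more participants, or a reduced model. The harm is possible, not likely.

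**The wording gives latitude.** Section 8.5.7 asks for an analysis similar to, not identical with, the QoL-B one, and the convergence rules referred to in 8.3.5.1 permit a switch to a parametric covariance. That is true, but neither provision addresses an empty arm, or a model that converges with too small a standard error.

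**It is exploratory.** This is correct. The endpoint is outside the 12 hypotheses in SAP 6.3, and SAP 3.2 describes the adolescent cohort as serving safety, exposure and directional trends.

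**Conclusion.** The point holds as a minor one. As written, SAP 8.5.7 prescribes a placebo comparison that will probably be non-estimable at the PCD shares in the protocol's own background (0.4 to 4.4 respondents, 39% to 92% chance of none on placebo). At larger sizes its intervals are too narrow: roughly 70% coverage at 5:5:2, rising to about 91% at 16:16:8. The parameter count follows from the model alone. The empty-arm probabilities depend on the PCD share, and the coverage figures on the assumed correlation and covariate frequencies.

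No primary or secondary conclusion is affected. The risk is confined to a spurious exploratory statement about quality of life in adolescents with PCD.

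**What to change.** In SAP 8.5.7, remove the instruction to analyse QoL-PCD statistically in the manner of SAP 8.3.5.1. Replace it with by-participant listings and descriptive summaries of scores and changes from baseline, by treatment group and questionnaire version. State that no model-based comparison or p-value will be produced because participants are too few, which is the course SAP 11.2 takes for blood biomarkers.

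In Table 8, change this endpoint's summary from mean difference to mean absolute value and mean change from baseline, as already used there for EQ-5D-5L. At the same time, correct the section reference in that row from 8.5.10 to 8.5.7.

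The cost is a wording change and less programming. The loss is a formal comparison for one exploratory endpoint; directional trends remain visible in the descriptive tables.
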